9.1.3 Control subjects

Study Periods	Screening		Observation period	
	1	2	3	
Visit	1	2	3	
Time (week)	-1	0	3	
Proband Information and Informed Consent	x			
Demographics	x			
SCID	x			
In- /Exclusion Criteria	x			
Physical Examination	x			
Pregnancy Test	x			
Primary Variable SRRS		x	x	
Motor scales UPDRS, BFCRS, AIMS, IPAQ		x	x	
Actigraphy and coin rotation		x	x	
Posturography		x	x	
TMS cortical excitability		x	x	
Cerebral MRI		x	x	

Study events for controls

Visit	Information	Instrument used	Expected time
1 (Screening)	Check inclusion / exclusion criteria	CRF	5 min
	Demographic data	CRF	5 min
	Medical history	CRF	10 min
	Handedness	Edinburgh Handedness Inventory ¹⁰¹	5 min
	Pregnancy test	Urine based test	10 min
	Diagnoses ascertainment	SCID interview	60 min
2 (week 0)	Primary outcome	SRRS ⁹²	5 min
	Motor scales	Unified Parkinson's Disease Rating Scale (UPDRS) ¹⁰⁵ , Bush Francis Catatonia Rating Scale (BFCRS) ¹⁰⁶ , Abnormal Involuntary Movement Scale (AIMS) ¹⁰⁷	15 min
	Self Report	International Physical Activity Questionnaire (IPAQ) ⁹⁵	5 min
	Motor tests	Actigraphy and coin rotation	5 min
	Posturography	Kistler platform at Dept. of Neurology	30 min
	Cortical excitability	TMS paradigm with paired pulse stimulation	30 min
	Neuroimaging	MRI scan including structural T1, Arterial spin labelling, BOLD resting state and task fMRI	60 min
	3 (week 3)	Primary outcome	SRRS ⁹²
Motor scales		Unified Parkinson's Disease Rating Scale (UPDRS) ¹⁰⁵ , Bush Francis Catatonia Rating Scale (BFCRS) ¹⁰⁶ , Abnormal Involuntary Movement Scale (AIMS) ¹⁰⁷	15 min
Self Report		International Physical Activity Questionnaire (IPAQ) ⁹⁵	5 min
Motor tests		Actigraphy and coin rotation	5 min
Posturography		Kistler platform at Dept. of Neurology	30 min
Cortical excitability		TMS paradigm with paired pulse stimulation	30 min
Neuroimaging		MRI scan including structural T1, Arterial spin labelling, BOLD resting state and task fMRI	60 min

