5.4 Safety Outcomes

After each rTMS session, participants are inquired about stimulation side effects. After sessions 5, 10 and 15, we will apply a short rating scale to assess side effects according to the guidelines^{1,2}.

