9.2.4 Assessment of safety outcomes

9.2.4.1 Adverse events

After every rTMS session, participants are asked about new occurrence of adverse events. As example, they are inquired about sensations associated with the stimulation or headaches. The answers are recorded in the CRF. Furthermore, at each study visit during the intervention phase, i.e. after 5 rTMS sessions, patients will be inquired about adverse events using a standard questionnaire in the CRF².

In case the adverse event is not limited to stimulation, the participants will be asked at the next session (24 hours later), whether the adverse event still continues or when it was resolved. The frequency and type of adverse events will be reported in the publication of results.

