10. SAFETY

10.1 Medical Device Category A studies

Device deficiencies and all **adverse events (AE)** including all **serious adverse events (SAE)** are collected, fully investigated and documented in the source document and appropriate case report form (CRF) during the entire study period, i.e. from patient's informed consent until the last protocol-specific procedure, including a safety follow-up period. Documentation includes dates of event, treatment, resolution, assessment of seriousness and causal relationship to device and/or study procedure [ISO 14155, 6.4.1.].

Safety is assessed spontaneously at each stimulation session and in a structured set of questions at each visit during the intervention phase (after 5 stimulations). See 9.2.4. If adverse events occur, patients are followed-up with extra-visits after 14 days until the issue has resolved.

Typical adverse events to be expected by rTMS are:

- Mild pain or nausea (39 %)
- Mild headaches (28%)
- Mild neck pain (40%)

Rare events include hearing problems or local skin irritation.

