10.1.1 Definition and Assessment of safety related events

Adverse Event (AE)

Any untoward medical occurrence, unintended disease or injury or any untoward clinical signs (including an abnormal laboratory finding) in participants, users or other persons whether or not

related to the investigational medical device [ISO 14155: 3.2].

This includes events related to the investigational device or the comparator and to the procedures involved. For users or other persons this is restricted to events related to the investigational medical device.

Adverse Device Effect (ADE)

Adverse event related to the use of an investigational medical device [ISO 14155: 3.1].

This includes any adverse event resulting from insufficient or inadequate instructions for use, deployment, implantation, installation, operation, or any malfunction of the investigational medical device. This includes any event that is a result of a use error or intentional misuse.

Serious Adverse Event (SAE) [European regulation on medical devices 2017/745, art. 58].

Any adverse event that led to any of the following:

- (a) death,
- (b) serious deterioration in the health of the subject that resulted in any of the following:
 - (i) life-threatening illness or injury,
 - (ii) permanent impairment of a body structure or a body function,
 - (iii) hospitalisation or prolongation of patient hospitalisation,
 - (iv) medical or surgical intervention to prevent life-threatening illness or injury or permanent impairment to a body structure or a body function,
 - (v) chronic disease,
- (c) foetal distress, foetal death or a congenital physical or mental impairment or birth defect.

This includes device deficiencies that might have led to a serious adverse event if a) suitable action had not been taken or b) intervention had not been made or c) if circumstances had been less fortunate. These are submitted to the EC via BASEC within 7 days. A planned hospitalisation for pre-existing condition, or a procedure required by the protocol, without a serious deterioration in health, is not considered to be a serious adverse event.

Device deficiency

Inadequacy of a medical device related to its identity, quality, durability, reliability, safety or performance, such as malfunction, misuse or use error and inadequate labelling [ISO 14155: 3.15].

Health hazards that require measures

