11.4.5 Safety analysis

The study team will provide a descriptive analysis of all reported adverse events. The analysis will focus on the type of event, duration, and timing and relate the number of observed events to the number of rTMS sessions administered. Furthermore, the frequency of adverse events will be compared between treatment arms of the trial.

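### Visits holding 278 of 454 planned excitability-TMS sessions, including all 80 in controls, have no adverse event entry, and the per-session safety figure counts rTMS sessions alone

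*Combined protocol and SAP*

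**What the plan says.** **Collection rule.** Section 10.1 has all adverse events documented "during the entire study period, i.e. from patient's informed consent until the last protocol-specific procedure, including a safety follow-up period", with their causal relation to the device or to a study procedure. Section 10.1.1 defines an adverse event for participants in general and adds: "This includes events related to the investigational device or the comparator and to the procedures involved".

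**Planned questions.** Section 5.4 states: "After each rTMS session, participants are inquired about stimulation side effects". Section 9.2.4.1 repeats this ("After every rTMS session, participants are asked about new occurrence of adverse events") and adds a questionnaire: "at each study visit during the intervention phase, i.e. after 5 rTMS sessions, patients will be inquired about adverse events". Both prompts follow rTMS.

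**Schedules.** The grid for groups 1-3 (9.1.1) ticks adverse events at weeks 0, 1, 2 and 3. The waiting-group grid (9.1.2) ticks weeks 3, 4, 5 and 6. The control grid (9.1.3) has no such row, and its event list has no side-effect line. Controls nevertheless have the "TMS paradigm with paired pulse stimulation" for 30 minutes and an MRI at both visits. Excitability is measured with the same device model that delivers the rTMS (8.1.1, 9.2.2.3).

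**Analysis.** Section 11.4.5 describes all reported events, will "relate the number of observed events to the number of rTMS sessions administered", and compares frequencies between treatment arms. Controls are not mentioned.

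**The concern.** The collection rule covers every study procedure, but the points at which somebody is scheduled to ask follow the rTMS course. Week 0 shows this. Groups 1-3 and the waiting group have the same excitability test and MRI that week, but only groups 1-3, who then start rTMS, have an adverse event tick.

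Two things are at stake. First, events after excitability TMS or MRI in healthy volunteers, for whom section 3.7 expects no personal benefit, depend on spontaneous report as far as the protocol text shows. The same holds for patients at the unticked visits. Second, the numerator in 11.4.5 takes all reported events, while the denominator counts one type of exposure. A headache after excitability testing, or any event in a control, would be set against rTMS sessions that did not cause it.

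**Working it through.** **Inputs.** There are 22 patients per arm, hence 66 in groups 1-3 and 22 in the waiting group, and 40 controls (synopsis). Each patient has 15 rTMS sessions (8.1). Visit weeks come from the grids in 9.1.1 to 9.1.3. Full attendance is assumed.

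**1. Check of the grid reading against a stated total.** MRI scans: 66 × 2 + 22 × 3 + 40 × 2 = 132 + 66 + 80 = 278. This is the figure in 12.2.1.1, so the grids are being read as the authors meant them, with controls scanned twice.

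**2. Excitability sessions with and without an adverse event tick at the visit.**

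| Group | n | Excitability weeks | Sessions | Ticked weeks among these | Sessions at unticked visits |
|---|---|---|---|---|---|
| 1-3 | 66 | 0, 3, 6, 24 | 66 × 4 = 264 | 0, 3 | 66 × 2 = 132 |
| Waiting | 22 | 0, 3, 6, 9, 24 | 22 × 5 = 110 | 3, 6 | 22 × 3 = 66 |
| Controls | 40 | 0, 3 | 40 × 2 = 80 | none | 40 × 2 = 80 |
| Total | 128 | | 454 | | 278 |

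Unticked share: 278 / 454 = 61%. In patients alone: (132 + 66) / (264 + 110) = 198 / 374 = 53%. At ticked visits: 454 − 278 = 176, or 39%. That 278 is also the number of MRI scans is a coincidence; the two counts refer to different visits.

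**3. MRI scans at unticked visits.** These are the waiting group at week 0 (22) and controls at both visits (80): 102 / 278 = 37%. All of them are also excitability visits, so no further visit is involved.

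**4. The tick count is generous to the plan.** Groups 1-3 have a tick at week 0, but the visit 2 event list and section 9.3.2 contain no side-effect step. The waiting group's week 3 event list has none either. Together these hold 66 + 22 = 88 of the 176 sessions at ticked visits. They are left on the ticked side because rTMS starts in those weeks and the per-session question follows. Section 9.3.5, for weeks 6 and 24, has no side-effect step, in line with the empty grid cells.

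**5. Denominator in 11.4.5.** Planned rTMS sessions: 88 × 15 = 1,320. None of the 454 excitability sessions, none of the 278 scans and no control is in it, while the numerator is not limited to events after rTMS.

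**The case against.** The strongest reply is that section 10.1 already obliges the team to collect every event to the end, with causality rated against study procedures, and that a grid row adds little. Section 9.2.5 also requires an adverse event assessment in anyone who stops early. The grids tick adverse events at weeks 0 and 3 in groups 1-3 and at weeks 3 and 6 in the waiting group, visits with both excitability TMS and MRI. It would therefore be wrong to infer that adverse event questions are tied to rTMS sessions and nothing else. What remains is that 10.1 states an obligation and then refers to 9.2.4 for how it is met, and 9.2.4.1 gives no prompt for controls or for the follow-up excitability visits. Section 10.1 also starts the period at the patient's consent, so its reach to controls is not explicit.

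A control version of the CRF is listed in the appendices but not shown. It may contain an adverse event page. This stands, and it limits the point to the protocol text.

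On the analysis, the rTMS-session denominator suits an objective about tolerability of rTMS (4.4). The three groups treated at once share the same excitability schedule, so their comparison is not distorted. Events that nobody asks about are unlikely to inflate a numerator. Recorded causality would allow test-related events to be separated. All of this is fair and is why the effect is probably small. But 11.4.5 does not say that the separation will be made.

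Resting motor threshold is determined before each rTMS session (8.2.1), so some measurement pulses belong to every session. The preceding procedure therefore has to mean the rTMS session as a whole, or a separate excitability or MRI session.

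**Conclusion.** The point holds as an inconsistency between the collection rule in 10.1 and what 9.1.1 to 9.1.3, 9.2.4.1 and 11.4.5 provide for. With full attendance, 278 of 454 planned excitability sessions (61%), including all 80 in controls, and 102 of 278 MRI scans (37%) fall at visits with no adverse event tick. The counts rest on the grids as extracted, which reproduce the stated scan total exactly. The mismatch between numerator and denominator is real but cannot be sized, because the documents give no event rate for excitability testing. It is probably small. The sample size and the primary analysis are not affected. This is a cheap improvement, not a serious fault.

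Stronger readings are tempting, and the documents do not support them:

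- That the control schedule contradicts 10.1.1. That section defines an adverse event and schedules nothing; the tension is with 10.1.
- That the reported figure departs from the one in 4.4. Section 4.4 names tolerability and states no rate.
- That 454 / (454 + 1,320) = 26% of TMS sessions escape safety questioning. Of the 454, 176 fall at ticked visits, and the 1,320 include 22 × 15 = 330 sham sessions that emit no magnetic pulse.
- That controls also need a concomitant therapy row. Section 8.7 concerns treatment that patients receive from their physicians.

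**What to change.** 1. In 9.1.3, add an adverse event entry at control visits 2 and 3. In the patient schedules, add it at weeks 6 and 24 for groups 1-3 and at weeks 0, 9 and 24 for the waiting group. Extend 9.2.4.1 to match, and state in 10.1 that the rule covers controls. If the control CRF already has the page, only the protocol text needs changing.
2. Add one CRF field that records which procedure preceded each event: rTMS session, excitability session or MRI.
3. In 11.4.5, count only events following rTMS sessions in the per-rTMS-session figure. List events after measurement procedures, and events in controls, separately.

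Cost: one field, one extra summary line, no added visits or staff. A short question of about a minute (an assumption) at the 278 planned visits concerned comes to 278 minutes, under 5 hours over the whole trial. With the 5 minutes that the event lists allow for a side-effect check, it is 278 × 5 = 1,390 minutes, about 23 hours.

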9.2 Assessments of outcomes

Assessors of outcome variables will be psychologists or psychiatrists of master-degree-level. All assessors will be trained by the PI to use the instruments correctly and to assure interrater reliability. Weekly staff meetings will ensure conformity in procedures. All assessments will be conducted blind to

rTMS treatment.

9.2.1 Assessment of primary outcome

The Salpêtrière Retardation Rating Scale (SRRS) is applied at each visit from baseline to follow-up. The scale is described in section 5.1. Raters will be trained to use the scale and blind to rTMS treatment. The score of each of the 15 items is recorded in the CRF.

9.2.2 Assessment of secondary outcomes

9.2.2.1 *Clinical outcomes*

The change in motor syndromes from baseline is assessed at several visits (see 9.1). Trained raters blind to treatment will assess motor behaviour in standardized examinations with clinical rating scales. Parkinsonism is assessed with the Unified Parkinson's Disease Rating Scale (UPDRS)¹⁰⁵, of which we will only assess part III, the current motor behaviour. Catatonia will be assessed with the Bush Francis Catatonia Rating Scale (BFCRS)¹⁰⁶, an 24 item rating scale specifically designed for this purpose. The timeframe of observation is the last week. Finally, dyskinesia will be monitored with the standard rating scale for this issue, the Abnormal Involuntary Movement Scale (AIMS)¹⁰⁷, a 7 item scale following a standardized examination. All motor rating scales are the gold standard of their kind.

The change of general schizophrenia symptoms is assessed with the Positive And Negative Syndrome Scale (PANSS)⁹³. The 30 item scale is the widely used standard assessment following a standardized clinical interview. Change in negative symptoms is specifically assessed with the Brief Negative Symptom Scale (BNSS)⁹⁴, which allows monitoring relevant dimensions of negative symptoms such as apathy and diminished expression. Furthermore, we will apply the self-evaluation of negative symptoms (SNS)⁹⁶, a valid and reliable 20 items questionnaire to capture the subjective experience of negative symptoms.

9.2.2.2 *Behavioral outcomes*

Objective gross motor behaviour will be assessed using continuous wrist actigraphy for 24 hours. The actigraphs (empathica e4) will be worn on the wrist of the non-dominant arm. Data is stored as logged electronic file. This measure is sensitive to altered motor behaviour and has been successfully applied in many studies of [name] team^{27, 35, 49, 50, 108-111}. Patients will fill a sleep activity protocol to enable separation of sleep from wake periods during recording. This also allows to check data for consistency and plausibility, because measurements are continuously performed also in periods when participants are not observed.

The fine motor performance is assessed with the coin rotation task. In this task, participants are asked to rotate a .50 CHF coin between thumb, index and middle finger as fast as possible for a total of 30 seconds. The performance is recorded on video and later analysed offline. Analysis includes the number of half turns and the number of coin drops according to a validated formula^{51, 52, 112}.

Self-ratings of physical activity will be conducted with the 7-item International Physical Activity Questionnaire (IPAQ)⁹⁵, which has a German Version and has great psychometric properties. The ratings cover the past 7 days and allow calculating the energy expenditure and total activity.

9.2.2.3 *Physiological outcomes*

Measures of cortical excitability will be assessed as one of the important physiological outcome parameters. Measurements will be conducted with a MagPro R30 (MagVenture, Inc. Atlanta GA, USA). Single pulse and paired pulse TMS protocols will be conducted to measure short-interval intracortical inhibition (SICI) at 1 msec interstimulus interval (ISI) and 3msec ISI, intracortical facilitation (ICF) at 7 msec ISI and 15 ms ISI, resting motor threshold (RMT), and 1 mV motor evoked potential (MEP), according to standard protocols^{67, 113}

Posturography will be conducted at the Department of Neurology ([name]). The assessments of postural sway will be scheduled immediately before or after the MRI acquisition, because this is also located at the Inselspital Bern. Mean postural sway will be calculated as outcome variable for postural stability^{53, 114}. The Kistler platform will be used to calculate of the pressure dependent fluctuation (x-, y-, z- axis) of the bodies' centre of gravity¹¹⁵. Participants will be measured standing with eyes open and eyes closed according to standard procedures.

9.2.2.4 *Neuroimaging outcomes*

Neuroimaging will be acquired twice, at baseline and week 3. MRI acquisition will be performed at a

3T Siemens Magnetom Trio scanner at the Institute of Diagnostic and Interventional Neuroradiology, Bern (local collaborator [name]. med. [name]). The 64-channel head coil will be used for all MRI images. First, high-resolution T1-weighted MR images will be obtained using a 3D magnetization-prepared rapid two-gradient-echo with 2 inversion times (MP2RAGE) sequence. fMRI will be performed using a multi-slice multi-band T2*-weighted echo planar imaging (EPI) sequence for resting state and during task execution. Prior to the fMRI images a B0 will be acquired for corrections of putative field inhomogeneity. Afterwards, we will perform acquisition of cerebral blood flow (CBF) at rest using a pseudo-continuous arterial spin labelling (pCASL) sequence. Moreover, we will acquire a M0 image (M0 equilibrium magnetization of water signal) for the quantification of CBF and a B0 for corrections of putative field inhomogeneity. Finally, a set of diffusion-weighted images (DWI) that will allow reconstructing fiber tracts using the model based on diffusion tensor imaging (DTI).

Anatomy (MP2RAGE) The optimized acquisition parameters were as follows: 176 sagittal slices, 256 × 224 matrix (with a non-cubic field of view (FOV) of 256 × 224 mm², yielding a nominal isotropic resolution of 1 mm³), 5000 ms repetition time (TR), 2.98 ms echo time (TE), 700 ms and 2500 ms inversion time (TI), flip angle 4° and 5°, GRAPPA acceleration factor 3 and a 8:22 min total acquisition time.

B0-map - The 48 EPI interleaved axial oblique slices will be positioned exactly like the fMRI slices with exactly the same slice geometry. Two amplitude and a phase image will be recorded in each subject (TR = 520 ms, TE1 = 4.92 ms, TE2 = 7.38 ms). The acquisition time will last 1 min 40 sec.

fMRI - The 48 EPI interleaved axial oblique slices will be positioned in-line with the bi-commissural axis with the following parameters: TR = 500 ms, TE = 30 ms, FA = 90, slice thickness = 3.6 mm, gap thickness = 0 mm, matrix size = 64 x 64 mm, FOV 230 x 230 mm² resulting in a iso-voxel dimension of 3.6 mm x 3.6 mm x 3.6 mm. The sequence is driven in a 3D PACE mode (Siemens Erlangen) to enable prospective motion correction. With these sequence parameters we will cover the whole brain including the cerebellum. In total, first 720 dynamic scans will be collected for resting state fMRI (total of 6 mins) and subsequently 1200 dynamic scans will be collected during the conduction of the task (total of 10 mins). The task will consist of four blocks including two active paced blocks, a passive listening block and rest. All blocks except rest will be paced with a continuous 2Hz auditory cue. The two active blocks are **right hand finger tapping** (index finger vs. thumb) and **sequential finger-thumb opposition** (all fingers of the right hand vs. thumb). These tasks have produced reliable activation of SMA, M1, basal ganglia, and cerebellum in healthy subjects and are easy enough to be performed by schizophrenia patients with PS^{62, 64, 65, 116, 117}. During one run, we will alternate active and passive blocks, i.e. finger tapping – listening – sequential finger opposition – rest. Each block will last for 15 s and each run takes 1 min. We will alternate the active blocks between runs. A total of 10 runs will be conducted. Instructions will be presented on a video goggle system. Cue tones will be delivered via headphones. Participants will be instructed and trained on the task outside the scanner.

pCASL - The 30 EPI interleaved axial oblique slices will be positioned in-line with the bi-commissural axis and acquired in sequential order with the following parameters: TR = 3000 ms, TE = 12 ms, FA = 90, slice thickness = 8.0 mm, gap thickness = 0 mm, matrix size = 64 x 64 mm, FOV 256 x 256 mm² resulting in a voxel dimension of 4.0 mm x 4.0 mm x 8.0 mm. the sequence will additionally have the following parameters: bolus duration = 700 ms, inversion time = 2200 ms. In total 100 images will be acquired lasting in total 6 min.

